## Analysis plan

### Continuous Outcome Measures

The study protocol pre-specifies the use of linear mixed models for the analysis of the continuous outcome measures (i.e., all measures presented in the paper except for number of healthcare consumption and accelerometer measurement of physical activity and blood samples).

### Analysis of between-group changes

Three measurement points will be available for analysis. Baseline (i.e., before randomization), post-treatment (post; i.e., immediately after treatment), and 3-month follow-up (3mfu) after post-treatment. The 3-month follow-up is the pre-determined primary endpoint. To utilize all available data, all three measurement points from all randomized patients will be included in the analysis. The model will include group, time, and group-by-time interaction effect as fixed effects. Time will be entered as a factor/categorical variable with three levels, baseline, post, and 3mfu, with baseline as the reference category. Thus, the model estimates separate interaction effects for post and 3mfu, allowing us to investigate the relative change from baseline between the groups at both post and 3mfu. Inference about treatment effect at the primary endpoint will be based on the p-value of the group-by-3mfu interaction effect, at a significance alpha-level of .05. The mixed models will also include a random intercept to account for the within-individual dependence between the individual observations over time.

Between group effect sizes (Cohen's d) will be calculated as the interaction effects (group-by-post and group-by-3mfu) divided by the baseline standard deviation for the respective measure. To obtain 95% confidence intervals for the effect sizes, we will bootstrap the mixed models analysis 5,000 times. The bootstrap sampling will be performed at the individual level, i.e., each sample included a random sampling (with replacement) of all randomized individuals. Each time an individual is selected, all their observations will be included with a new clustering identifier. For each bootstrap sample, the mixed models will rerun to obtain the interaction effects and the baseline standard deviation will be recalculated to obtain the post and 3mfu effect sizes. The 5,000 bootstrapped effect sizes are then used to obtain bias-corrected and accelerated 95% confidence intervals.

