### Analysis of healthcare consumption

Regarding healthcare consumption data (i.e., the number of healthcare visits during the last three months), we expect that the distribution of scores will not be suitable for a linear mixed model as described above, since number of healthcare visits is a count variable. If appropriate, we will use statistical a model more suitable for skewed count data, generalized mixed model using the Poisson distribution with a log link function random intercept. Confidence intervals for fixed effects will be calculated based on the guidelines provided at <https://stat.ethz.ch/pipermail/r-sig-mixed models/2011q1/015910.html>. Effect sizes will not be calculated for this data and instead we will exponentiate the group-by-time interaction effects (between-groups analyses) and Time effects (within-group analyses) to get the percentage reduction in healthcare consumption. In other respects, between- and within group analyses will be performed with the same model specifications as the continuous outcomes.

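### The primary mixed model estimates a baseline group difference that randomisation sets to zero; a common baseline mean with an unstructured covariance would usually sharpen the group-by-3mfu estimate

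*SAP*

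**What the plan says.** The SAP section on between-group changes uses three occasions: "Baseline (i.e., before randomization), post-treatment (post; i.e., immediately after treatment), and 3-month follow-up (3mfu) after post-treatment". Time is categorical with baseline as the reference level, and the fixed effects are given by "The model will include group, time, and group-by-time interaction effect as fixed effects". The only dependence structure is this: "The mixed models will also include a random intercept to account for the within-individual dependence between the individual observations over time".

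The stated purpose is "allowing us to investigate the relative change from baseline between the groups at both post and 3mfu", and the primary test is fixed by "Inference about treatment effect at the primary endpoint will be based on the p-value of the group-by-3mfu interaction effect". Effect-size intervals come from 5,000 bootstrap refits of the same model.

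The SAP section on continuous outcome measures applies linear mixed models to "all measures presented in the paper except for number of healthcare consumption and accelerometer measurement of physical activity and blood samples". The healthcare consumption section then carries the specification over to the count model: "In other respects, between- and within group analyses will be performed with the same model specifications as the continuous outcomes". Nowhere does the SAP impose a common baseline mean or adjust for baseline in another way.

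**The concern.** With baseline as reference level, the group coefficient is the baseline difference between arms. Because baseline precedes randomisation, both arms have the same population mean there, and any observed difference is chance. The planned model subtracts that whole chance difference from the 3mfu difference. Only the part of it that predicts the 3mfu value needs to come off; the rest adds noise.

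The noise falls on the coefficient that carries the primary inference. The covariance matters as well. A random intercept implies equal variances and one correlation at all three occasions, so a remedy that changes only the fixed effects may do harm.

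**Working it through.** **Inputs.** From the SAP: the fixed effects, time coding, random intercept, timing of baseline, primary coefficient and alpha of .05 (taken as two-sided). Assumed, because the SAP gives none: 1:1 allocation with n per arm, correlation r from .3 to .9, the ratio k of the post and 3mfu SDs to the baseline SD, and dropout. There is no stated figure to reproduce.

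**Step 1: formulas, complete data, large sample.** Let s0 and s3 be the baseline and 3mfu SDs. Variances are in units of 2/n.

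- Planned model: group-by-time is saturated, so the coefficient is the difference in mean change, with variance s0² + s3² − 2·r·s0·s3.
- Common baseline mean with unstructured covariance: s3²(1 − r²).
- Saving: (s0 − r·s3)², never negative, and zero only when r·s3 = s0.

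**Step 2: numbers (s0 = 1, s3 = k).**

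- k = 1, r = .5: planned 1 + 1 − 1 = 1.00; proposed 1 − .25 = .75; ratio .75. With equal SDs the ratio is always (1 + r)/2.
- k = 0.8, r = .5: planned 1 + .64 − .80 = .84; proposed .64 × .75 = .48; ratio .571.
- k = 1.3, r = .7: planned 1 + 1.69 − 1.82 = .87; proposed 1.69 × .51 = .862; ratio .991.

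Variance ratio, proposed over planned:

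| Setting | r = .3 | r = .5 | r = .7 | r = .9 |
|---|---|---|---|---|
| k = 0.8 | .502 | .571 | .628 | .608 |
| k = 1 | .650 | .750 | .850 | .950 |
| k = 1, 20% of 3mfu missing completely at random | .697 | .786 | .873 | .958 |
| k = 1.3 | .805 | .912 | .991 | .917 |
| k = 1.5 | .871 | .964 | .998 | .777 |

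As an illustration only: at k = 1, r = .5, the SE falls by a factor √.75 = .866, so a trial with 80% power under the planned model would have about 90%.

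**Step 3: common baseline with the random intercept kept.** Take k = 1.3, r = .7.

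- The fitted random-intercept model settles at the average variance (1 + 1.69 + 1.69)/3 = 1.46 and the average covariance .7 × (1.3 + 1.3 + 1.69)/3 = 1.001. Its working correlation is 1.001/1.46 = .686.
- The estimate is then the 3mfu difference minus .686 times the baseline difference. True variance: 1.69 + .470 − 2 × .686 × .7 × 1.3 = .912. Against the planned .87 the ratio is 1.049, a loss.
- The model reports 1.46 × (1 − .470) = .774. The SE is understated by √(.774/.912) = .921, and the nominal 5% test rejects about 7.1% of the time.

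Across r = .3, .5, .7, .9 at k = 1.3:

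| | r = .3 | r = .5 | r = .7 | r = .9 |
|---|---|---|---|---|
| Ratio to planned variance | .810 | .930 | 1.049 | 1.155 |
| Type I error, common baseline + random intercept | 6.9% | 6.9% | 7.1% | 7.9% |
| Type I error, planned model | 4.2% | 4.2% | 4.4% | 5.1% |

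**Step 4: unequal correlations.** Take equal SDs and correlations .5 (baseline–post), .4 (baseline–3mfu), .7 (post–3mfu). The planned model uses the average, 1.6/3 = .533, and reports 2(1 − .533) = .933 where the truth is 2(1 − .4) = 1.20. Its type I error is 8.4%. It is 7.3% with a common baseline and random intercept, and nominal in large samples with the unstructured covariance, where the variance ratio is (1 + .4)/2 = .70.

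**Step 5: finite samples.** REML, 60 per arm (assumed), 3,000 null trials, Monte Carlo SE 0.4 points. Type I error uses a normal critical value; t on 118 df is in brackets.

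| Setting | Proposed: ratio | Proposed: type I | Planned: type I |
|---|---|---|---|
| r = .7, k = 1.3, complete | .99 | 5.8% (5.4%) | 4.6% |
| r = .7, k = 1.3, 20% missing | 1.01 | 6.4% (6.2%) | 5.7% |
| r = .5, k = 1, 20% missing | .81 | 5.8% (5.5%) | 5.4% |
| r = .7, k = 1, 20% missing | .89 | 5.6% (5.4%) | 4.9% |

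**The case against.** The planned model is standard, internally consistent and unbiased for its stated target, so choosing another is a matter of efficiency. That is correct, and neither bias nor a power shortfall is alleged.

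The gain is also unknown for this trial and can be nil. At r = .7 and k = 1.3 it is under 1% in large samples, and the simulated ratio with 20% missing is 1.01. This stands, and it is why the claim is limited to usually.

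In all four finite-sample settings the proposed model's type I error was somewhat above the planned model's, and the recommended Kenward-Roger correction was not itself simulated. A separate simulation of the worst setting (4,000 null trials) gave 6.0% with a normal critical value and 5.7% with t on 118 df. The inflation is small, but nominal error at this size has not been shown.

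The 8.4% figure in Step 4 concerns the covariance and not the baseline term. It supports the second half of the remedy only.

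Finally, the protocol is not shown and may itself fix the group term or the random intercept. That affects where the change is recorded, not whether it helps.

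**Conclusion.** The point holds as a worthwhile improvement. Data already collected would, in most plausible settings, give a more precise primary estimate of the same quantity, since equal population baseline means leave the between-arm contrast at 3mfu unchanged. Over the assumed range (r from .3 to .9, k from 0.8 to 1.5) the large-sample variance ratio runs from .50 to almost 1; at equal SDs and r = .5 it is .75. These figures rest on assumed correlations, SDs, dropout and 1:1 allocation, none of which the SAP gives. They apply to the linear mixed models and not to the count model. The benefit is secure only if the baseline constraint and the covariance are changed together.

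**What to change.** In the between-group section, for the outcomes analysed by linear mixed model:

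1. Drop the group main effect. Fit time plus two hand-coded indicators, group-by-post and group-by-3mfu, with baseline kept in the outcome vector so that all randomised patients stay in. Merely deleting the main effect from a factor formula re-creates a baseline group term.
2. Replace the random intercept with an unstructured 3×3 within-person covariance and use small-sample degrees of freedom, for example Kenward-Roger. Do not adopt item 1 without item 2.
3. Keep the group-by-3mfu coefficient as the primary test and the planned model as a sensitivity analysis.
4. The SAP says "For each bootstrap sample, the mixed models will rerun to obtain the interaction effects"; use the new model there, and count and report refits that do not converge.
5. State in the healthcare consumption section that the change does not extend to the count model. The one-arm within-group model is likewise outside it.

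The cost is SAP wording, two indicators and 6 covariance parameters instead of 2, repeated in 5,000 refits. It needs no new data and loses no patients. The downsides are possible convergence failures in some refits and slight small-sample inflation if a normal critical value is used. If the protocol also fixes the group term or the random intercept, amend it too. In either case, make the change before anyone sees data by arm.

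### The primary p-value rests on a random-intercept-only model, so its .05 level holds only if the baseline-to-3-month change variance matches the average over all visit pairs

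*SAP*

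**What the plan says.** The SAP section *Analysis of between-group changes* names a single primary time point: "The 3-month follow-up is the pre-determined primary endpoint". Its fixed part is clear: "The model will include group, time, and group-by-time interaction effect as fixed effects", and "Time will be entered as a factor/categorical variable with three levels, baseline, post, and 3mfu, with baseline as the reference category". The decision rule is "Inference about treatment effect at the primary endpoint will be based on the p-value of the group-by-3mfu interaction effect, at a significance alpha-level of .05".

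For dependence between a person's visits the section gives one sentence: "The mixed models will also include a random intercept to account for the within-individual dependence between the individual observations over time". The SAP names no residual covariance structure, random slope, visit-specific variance or robust standard error, and no sensitivity analysis for this test. The section *Analysis of within-group changes in the MI-CBT group* repeats the same sentence for the four-visit model.

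A bootstrap is planned, but for another purpose: "To obtain 95% confidence intervals for the effect sizes, we will bootstrap the mixed models analysis 5,000 times". Its unit is the person: "The bootstrap sampling will be performed at the individual level".

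**The concern.** With categorical time and independent, constant-variance residuals, a random intercept is compound symmetry: every pair of visits has the same correlation and every visit the same variance. The model then has one change variance for all three pairs (baseline–post, post–3 months, baseline–3 months) and estimates it by pooling. The primary test concerns only the last pair.

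Baseline and 3 months are the furthest apart and have treatment between them, so they could well be the least correlated pair. If so, with equal SDs, the pooled variance is too small for the primary contrast and the test rejects too often. In other patterns it is too large and power is lost. Either way, the true level of the only primary test depends on a correlation pattern that the plan neither states nor allows for.

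There is also a reporting consequence. The p-value depends on the covariance assumption, while the person-level bootstrap interval beside it largely does not. The two can disagree more often than they need to, for example p below .05 next to an interval that includes zero.

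**Working it through.** **Inputs from the SAP.** Three visits with categorical time; group, time and group-by-time effects; a random intercept; alpha .05 for the group-by-3-month term.

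**Assumptions.** Two-sided test (the SAP does not say); independent, equal-variance residuals; the same covariance in both arms; complete data unless noted. All correlations, SDs and sample sizes below are assumed, because the SAP gives none.

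**Formulas.** For visits i and j with SDs s and correlation r, the change variance is V(i,j) = s_i² + s_j² − 2·r·s_i·s_j. With complete data the estimated effect is the between-group difference in mean change, so only its standard error is in question.

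- Change variance used by the random-intercept model: the mean of V over the three pairs.
- True change variance for the primary contrast: V(baseline, 3 months).
- SE ratio = √(mean V / V(baseline, 3 months)).
- Actual alpha = 2·Φ(−1.96 × SE ratio).

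**The plan's own figure first.** With all correlations .6 and equal SDs, each V is 2(1 − .6) = 0.8. The ratio is 1 and alpha is 5.0%, so the stated level reproduces under compound symmetry.

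**A worked departure.** For .6/.75/.5 (baseline–post / post–3 months / baseline–3 months) the three V are 0.8, 0.5 and 1.0, with mean 0.767. The SE ratio is √(0.767/1.0) = 0.876, and alpha = 2·Φ(−1.96 × 0.876) = 8.6%.

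| Correlations | SDs | Mean V | V(baseline, 3 months) | SE ratio | Actual alpha |
|---|---|---|---|---|---|
| .6/.6/.6 | equal | 0.800 | 0.800 | 1.000 | 5.0% |
| .5/.7/.6 | equal | 0.800 | 0.800 | 1.000 | 5.0% |
| .6/.6/.55 | equal | 0.833 | 0.900 | 0.962 | 5.9% |
| .6/.65/.55 | equal | 0.800 | 0.900 | 0.943 | 6.5% |
| .6/.7/.5 | equal | 0.800 | 1.000 | 0.894 | 8.0% |
| .6/.75/.5 | equal | 0.767 | 1.000 | 0.876 | 8.6% |
| .7/.7/.49 (AR(1)) | equal | 0.740 | 1.020 | 0.852 | 9.5% |
| .5/.7/.5 | 1/1.2/1.2 | 1.115 | 1.240 | 0.948 | 6.3% |
| .6/.6/.6 | 1/1.2/1.2 | 1.051 | 1.000 | 1.025 | 4.5% |
| .5/.5/.6 | equal | 0.933 | 0.800 | 1.080 | 3.4% |
| .5/.5/.7 | equal | 0.867 | 0.600 | 1.202 | 1.9% |

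**Null simulation, complete data, 20,000 runs per setting** (random intercept vs unstructured):

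- .6/.75/.5: 8.3% vs 4.8% (N=60), 8.4% vs 4.9% (N=120), 8.8% vs 5.0% (N=240).
- .5/.5/.6: 3.4% vs 4.9%, 3.5% vs 5.0%, 3.4% vs 5.0% at the same sizes.

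A larger sample does not remove the error. A separate simulation with 60 per arm compared the random intercept with an unconstrained change variance. It gave 9.6% vs 5.0% for .7/.7/.49, 2.1% vs 5.2% for .5/.5/.7, and 5.2% for both under compound symmetry.

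**With 15% of each follow-up missing.** A large-sample sandwich calculation gives the random-intercept test a level of 7.8% for .6/.75/.5 and 3.6% for .5/.5/.6. Simulated REML fits (N=120, missing at random) gave 7.4% vs 4.8% unstructured (1,156 runs) and 3.9% vs 6.2% (897 runs), with Monte Carlo error of about 0.6 to 0.8 points.

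**P-value against bootstrap interval** (null, N=120, 2,000 runs, 1,000 person-level resamples, BCa interval for d). For .6/.75/.5 the random-intercept p is below .05 in 8.1% of trials, the unstructured p in 5.3%, and the interval excludes zero in 5.2%. P below .05 beside an interval including zero occurs in 8.1 − 5.2 = 2.9% of trials. P-value and interval disagree in 2.9% with the random intercept and 0.9% with the unstructured model. Under compound symmetry the figures are 1.4% and 1.2%.

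**The case against.** The strongest reply is that the SAP contains no demonstrable error. It states a coherent, parsimonious and widely used model with one named contrast. Every correlation behind the figures above is assumed, and the level is exactly 5.0% in two of the patterns. Reaching 8% or more with equal SDs needs the baseline–3-month correlation to be about .2 or more below the post–3-month correlation. All of this stands: direction and size cannot be established from the document, and the claim is only that the standard error can be wrong.

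A second reply is that the residual structure is inferred. The section does not say that residuals are independent with constant variance, and the protocol, which is not shown, may say more. That is fair, but the stated reading is the usual default, and nothing in the SAP points elsewhere.

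A third is that the person-level bootstrap already supplies an interval largely robust to a wrong covariance. That is true of the interval, which excluded zero in 5.2% of null trials in the adverse pattern. But the SAP decides on the p-value: "Inference about treatment effect at the primary endpoint will be based on the p-value of the group-by-3mfu interaction effect". The bootstrap does not feed it.

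A fourth is that the unstructured model gave 6.2% in one missing-data simulation. With 897 runs the standard error at 5% is √(.05 × .95 / 897) = 0.73 points, so the excess is 1.2/0.73, about 1.6 standard errors, which is compatible with noise. The run counts there are irregular, so those simulations are weaker evidence than the complete-data results.

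**Conclusion.** The point holds. As specified, the level of the primary test depends on whether the variance of the baseline-to-3-month change equals the average over the three visit pairs, and nothing in the SAP protects the p-value if it does not. Across the illustrative patterns the actual level runs from 1.9% to 9.5%. It is 5.9% to 9.5% where SDs are equal and baseline and 3 months are the least correlated pair, and nominal under compound symmetry. The range assumes independent, constant-variance residuals, a two-sided test, complete data and equal covariance in the arms; the missing-data checks show the same direction with a somewhat smaller error. This is not a fatal flaw, since the error may be nil or conservative. It affects the only primary test and is cheap to remove, so it should be fixed before analysis. A covariance changed later would be a data-driven choice.

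**What to change.** In *Analysis of between-group changes*, replace the random-intercept sentence with wording such as:

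> Dependence among the three visits is modelled with an unstructured within-person covariance matrix, estimated by REML, with Kenward-Roger (or Satterthwaite) degrees of freedom. The bootstrap refits use the same model, and the number and handling of non-convergent replicates are reported. If the main fit does not converge, [one named fallback] is used.

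Name one fallback in advance. It can be the random-intercept model with small-sample-corrected cluster-robust standard errors, or primary inference from the planned person-level bootstrap applied to the interaction itself. Carrying the same covariance into the within-group section is optional, for consistency.

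The cost is a changed model specification, six covariance parameters instead of two, 5,000 unstructured refits per outcome, and a rule for non-convergence. P-values may move in either direction. A model-based p-value and a BCa interval for a ratio will still disagree occasionally (0.9% to 1.2% of null trials in the simulations above).

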### Analysis of within-group changes in the MI-CBT group

These analyses will be performed to investigate the long-term changes in the MI-CBT group compared to baseline. One long-term follow-up measurement points will be available at this point, 12 months after post-treatment (12mfu). To utilize all available data, we will also include the baseline, post, and 3mfu measurement points in the mixed-models analysis. Time will be entered as a factor/categorical variable with four levels, baseline, post, 3mfu, and 12mfu, with baseline as the reference category. Thus, the model estimated separate effects of time for post, 3mfu and 12mfu, allowing us to investigate the change from baseline in the MI-CBT group. The mixed models will also include a random intercept to account for the within-individual dependence between the individual observations over time.

Within-group effect sizes will be calculated by dividing the time effects by the baseline standard deviation and 95% confidence intervals are obtained by the same bootstrapping method used for the between-group effects.

### Analysis of healthcare consumption

Regarding healthcare consumption data (i.e., the number of healthcare visits during the last three months), we expect that the distribution of scores will not be suitable for a linear mixed model as described above, since number of healthcare visits is a count variable. If appropriate, we will use statistical a model more suitable for skewed count data, generalized mixed model using the Poisson distribution with a log link function random intercept. Confidence intervals for fixed effects will be calculated based on the guidelines provided at <https://stat.ethz.ch/pipermail/r-sig-mixed models/2011q1/015910.html>. Effect sizes will not be calculated for this data and instead we will exponentiate the group-by-time interaction effects (between-groups analyses) and Time effects (within-group analyses) to get the percentage reduction in healthcare consumption. In other respects, between- and within group analyses will be performed with the same model specifications as the continuous outcomes.

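### Healthcare visits: the only count model named is a random-intercept Poisson model, whose p-values are too small if visits vary within a person more than Poisson allows

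*SAP*

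**What the plan says.** The SAP section *Analysis of healthcare consumption* defines the outcome as "the number of healthcare visits during the last three months" and expects a linear mixed model not to suit it. It continues: "If appropriate, we will use statistical a model more suitable for skewed count data", and names that model as a "generalized mixed model using the Poisson distribution with a log link function random intercept". No other count model appears.

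Three further statements decide how inference is made:

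- The rest is carried over: "In other respects, between- and within group analyses will be performed with the same model specifications as the continuous outcomes". In *Analysis of between-group changes*, inference "will be based on the p-value of the group-by-3mfu interaction effect", at a level of .05.
- "Confidence intervals for fixed effects will be calculated based on the guidelines provided at" a web link. The content of that post is not in the SAP.
- The person-level bootstrap in *Analysis of between-group changes* has a stated purpose: "To obtain 95% confidence intervals for the effect sizes, we will bootstrap the mixed models analysis 5,000 times". For visits, however, "Effect sizes will not be calculated for this data", so the bootstrap does not reach this outcome.

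**The concern.** A Poisson model with a random intercept assumes that, given a person's own level, the variance of the count equals its mean. The intercept takes up lasting differences between heavy and light users of care, including the skewness they cause, so skewness alone does no harm. It does not take up person-specific fluctuation between windows, such as an illness episode or a referral that produces a cluster of visits. Such fluctuation is plausible for visits counted over three months, but the SAP has no data on it.

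The group-by-3mfu interaction, and the time effects in the MI-CBT group, compare people with themselves. Their precision therefore depends on exactly the variance component that the Poisson model fixes. If the true within-person variance is larger, the standard errors are too small, and a change in healthcare use is declared more often than 5% of the time when there is none. Nothing in the text requires anyone to look for this or says what to do if it is found.

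**Working it through.** **Inputs from the SAP.** Poisson mixed model with log link and random intercept; group, time (categorical) and group-by-time fixed effects; three time points for the between-group analysis; alpha .05 (taken as two-sided). The SAP gives no visit rate, dispersion or sample size, so there is no figure of its own to reproduce beyond the nominal 5%.

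**Assumptions.** φ is the within-person variance-to-mean ratio, varied from 1 to 3. The main simulation uses 60 per arm, a mean of 2 visits, a between-person log-SD of 0.7, and no treatment or time effect.

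**Step 1: the model's standard error.** With complete data and a free mean for each group-by-time cell, the interaction estimate is the log ratio of four cell totals T (each arm at baseline and 3mfu), with

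SE(model) = √(1/T₁ + 1/T₂ + 1/T₃ + 1/T₄).

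A quadrature fit of the mixed model agreed with this expression, for both estimate and SE, to at least 6 decimals. With 60 × 2 = 120 visits expected per cell, SE(model) ≈ √(4/120) = 0.183.

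**Step 2: the true standard error.** The same people supply both time points, so their stable levels cancel. If the within-person variance is φ × mean, the variance of each log total is about φ/T, and

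SE(true) ≈ √φ × SE(model).

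At φ = 2 this is 1.414 × 0.183 = 0.259.

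**Step 3: type I error.** The test rejects when |estimate|/SE(model) > 1.96, so

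type I error = 2 × [1 − Φ(1.96/√φ)].

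At φ = 2: 1.96/1.414 = 1.386, giving 16.6%. Sample size does not appear in the formula, so a larger trial does not help.

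**Step 4: simulation.** Poisson and negative binomial random-intercept models were fitted by maximum likelihood to the same data, with a Wald test at 1.96 and 6,000 runs per setting (Monte Carlo error 0.3 to 0.6 points).

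| φ | Formula | Poisson, group-by-3mfu | Poisson, one-arm time effect at 3mfu | Negative binomial, group-by-3mfu | True SE, group-by-3mfu |
|---|---|---|---|---|---|
| 1 | 5.0% | 5.0% | 4.9% | 4.6% | 0.184 |
| 1.25 | 8.0% | 8.0% | 8.4% | 5.5% | 0.206 |
| 1.5 | 11.0% | 10.7% | 10.9% | 5.4% | 0.227 |
| 2 | 16.6% | 16.4% | 16.3% | 4.8% | 0.260 |
| 3 | 25.8% | 26.0% | 27.0% | 5.4% | 0.327 |

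The Poisson model's own SE stayed at 0.184 to 0.186 throughout. With 120 per arm and φ = 1.5, its rejection rate was 11.5%.

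**Step 5: sensitivity to the assumptions.**

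- *Gamma-distributed extra variation* (between-person log-SD 0.7; 40, 80 or 150 per arm; 4,000 runs each). With none, rejection was 4.8% to 5.6%. With overdispersion parameters of 0.25, 0.5 and 1, it was about 13–14%, 21–23% and 33–34% at a mean of 2 visits, and about 22–23%, 33% and 45–47% at a mean of 4. Sample size made little difference.
- *Lognormal person-by-time fluctuation* (60 per arm, between-person log-SD 0.7, 8,000 runs each). With none, rejection was 4.9% to 5.2%. With log-SD 0.3 it was 6.5%, 8.0% and 12.2% at means of 1, 2 and 4 visits. With log-SD 0.5 it was 9.9%, 14.7% and 23.8%.

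The inflation does not depend on the mechanism. It is small when both the fluctuation and the visit rate are small.

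**The case against.** **The Poisson model is conditional.** Marked overdispersion could be taken as a reason not to use it. But the condition follows directly on the remark that a linear model will not fit, so it reads as the condition for leaving the linear model. It has no criterion and leads to no other count model. Any replacement would be chosen after seeing the data.

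**The p-value rule may not carry over.** The carried-over specification could mean only the fixed effects, time coding and random intercept, leaving intervals as the one inferential method stated for visits. That reading is possible, but the carry-over is of the analyses as a whole, so the p-value rule more naturally applies.

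**The linked post may give sound intervals.** This stands as a limit. The intervals share the defect only if the post builds them from the Poisson model's own standard error or likelihood, which cannot be checked here. The link is cited for intervals only, not for p-values or a dispersion check.

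**The sizes are not estimates for this trial.** This also stands. They show what happens over a range of φ. Near φ = 1 the inflation is slight, and with φ below 1 the test would err on the cautious side.

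**A dispersion check with a named fallback would do.** It would close the gap. Using the more general model from the start is simpler and avoids a choice that depends on the data.

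**Conclusion.** The point holds in its conditional form. The model as specified keeps the nominal 5% only if visits vary within a person no more than Poisson allows, and the SAP states neither a check of that assumption nor an alternative. If the assumption fails, type I error for the group-by-3mfu effect and for the MI-CBT time effects rises to about 8% at φ = 1.25, 11% at 1.5, 17% at 2 and 26% at 3. Those values rest on assumed dispersion, a two-sided test and complete data; the true φ in this trial is unknown. The claim covers the p-values for this one outcome, and the intervals only under the condition given above. It does not touch the outcomes analysed with linear mixed models. The change should be made, since it is cheap and protects any claim about reduced healthcare use.

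**What to change.** In *Analysis of healthcare consumption*, replace the Poisson specification with one of these:

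- a negative binomial mixed model with log link and a random intercept per person, stating the form of the variance function; or
- the Poisson mixed model with an added observation-level random effect.

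Keep the fixed effects as they are. State that both the p-value and the 95% interval for the rate ratio come from this model, in the between-group and the within-group analysis. Delete the opening condition (the first two words of "If appropriate, we will use statistical a model more suitable for skewed count data") or give it an explicit criterion; once the model allows for extra variation, it has little left to do. Optionally, extend the person-level bootstrap to the log rate ratio as a check on the interval.

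The cost is a few lines of SAP text, a change of family in the code and one extra parameter. When the simulated data were truly Poisson, the negative binomial SE averaged 1.016 times the Poisson SE, so intervals would be about 1.6% wider. If overdispersion is present, the SE grows by about √φ (1.22 times at φ = 1.5, 1.41 at 2, 1.73 at 3), which is the uncertainty the Poisson model leaves out.
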